6.3.2 Secondary Efficacy Clinical Endpoint(s)

Key secondary endpoints

• Normalized Sum of Pain Intensity Difference (PID, which equals the instantaneous NRS change from baseline) over 5 days (SPID₀₋₅). The Sum of Pain Intensity Difference (SPID) is to be calculated by multiplying the PID score at each post dose time point by the duration (in hours) since the preceding time point. The Normalized Sum of Pain Intensity Difference (SPID₀₋₅) is to be calculated as the SPID₀₋₅ divided by the total duration time..

Normalized
$$SPID_{0-5} = \frac{\sum_{i=1}^{9} (T_i - T_{i-1}) * PID_i}{T_9 - T_0}$$

where $T_0 = 0$, T_i – actual time and PID_i – Pain Intensity Difference score at time T_i . Pain Intensity Difference, in turn, is defined as $PID_i = PI_i - PI_0$ where PI_0 – Pain Intensity at time T_0 .

- Roland-Morris Disability Questionnaire^[5] (RMDQ) score improvement (%) from baseline to Day 5. Details of the scoring of the Roland-Morris Disability Questionnaire are provided in Section 17.1.
- Mobility evaluation^[6,7]: change from baseline to Day 5. The mobility evaluations (Schober's Test or Fingertip to Floor Test) are described in Section 17.2.
- Time to reach acceptable pain. Time from randomization to the first report of acceptable pain; if that event never occurs, the tine will be censored at the final visit.

Other secondary endpoints

- Time to reach no pain (NRS = 0). Time from randomization to the first report of NRS=0; if that event never occurs, the time will be censored at the final visit.
- Time course of PID (see above) over time from baseline to Day 5 on-site evaluation
- Time course of Pain relief over time from baseline to Day 5 (VRS)
- Normalized Sum of Pain relief over 5 days (TOTPAR₀₋₅). Total pain relief (TOTPAR) is calculated by multiplying the pain relief score at each post-dose time point by the duration (in hours) since the preceding time point. The Normalized Sum of Pain Relief (TOTPAR₀₋₅) is to be calculated as the Total Pain Relief divided by the total duration time.

Normalized TOTPAR₀₋₅ =
$$\frac{\sum_{i=1}^{9} (T_i - T_{i-1}) * PAR_i}{T_9 - T_0},$$

where $T_0 = 0$, T_i – actual time and PAR_i – Pain Relief score at time T_i .

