7.6 Clinical Procedures

The study will be performed in Investigational Sites and an online e-diary will be used.

A total of 2 site visits and 1 phone contact are planned during a maximum of 5 days of treatment and 6 days of total study duration.

7.6.1 Day 1, Visit 1

Clinical procedures on Day 1, Visit 1 include the following:

- Verification of eligibility
- Informed Consent Signatures
- Local Physical Examination

- Collection of Vital Signs to include: Respiratory rate, Heart rate, Temperature, Blood Pressure
- Collection of Demographics to include: Age, Gender
- Collection of relevant medical history and concomitant medications
- On-line daily e-diary will be explained and activated
- Urine pregnancy testing (for women of childbearing potential only)
- Causes and/or circumstances triggering the acute back pain
- Baseline Subject symptom self-assessment
 - Pain Perception (NRS): Numerical Rating Scale^[3] for pain assessments at baseline and at defined time points: 0-10 NRS; '0' representing "no pain" and '10' representing "worst pain imaginable
 - Instantaneous: pain at the moment of the evaluation
 - Average pain in the previous 12 hours.
 - Worst pain in the previous 12 hours
 - Least pain in the previous 12 hours
 - o Roland-Morris Disability Questionnaire (RMDQ)^[5]
- Baseline mobility assessment (physician)
- Randomization:
 - O Arm A: ITP FIRTECH: Patch application according to the instruction for use in Section 17.3: The patch has to stay in position for 5 days. If the patch is taken-off or if it fell off during the study duration, the subject is invited to replace the patch at home following the instruction for use. Subject is allowed to take-off the patch at any time in case of severe skin itchiness, irritation, or skin reaction and in this case the subject has to contact the study center.
 - o Arm B: no-patch: Subjects will be informed that they will not be assigned a patch in this study.
- All subjects are informed that rescue mediation (paracetamol, up to 2 g per day), while not encouraged, is allowed if necessary.
- All subjects will be informed of the prohibited medications.
- If rescue medication is taken, the exact moment(s) and the dose(s) have to be indicated in the e-diary.
- An explanation will be provided on how to use e-diary at home and providing all necessary access credentials
- All subjects will be requested to avoid bed rest and will be recommended to continue with a normal daily life activity.

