8.3.1.2 Secondary Analyses

Under the secondary analyses (key and other), descriptive and inferential analysis, where applicable, will be conducted for the following:

- Normalized Sum of Pain Intensity Difference (SPID₀₋₅): the descriptive and inferential analyses will be conducted for Day 5.
- Roland-Morris Disability Questionnaire^[5] (RMDQ) score: descriptive analysis will be conducted for the observed values at baseline and Day 5, as well as for change (improvement (%)) from baseline to Day 5. Inferential analysis will be conducted for change (improvement (%)) from baseline to Day 5.
- Mobility evaluation^[6,7]: descriptive analysis will be conducted for the observed values at baseline and Day 5, as well as for change from baseline to Day 5. Inferential analysis will be conducted for change from baseline to Day 5.
- Time to reach acceptable pain and time to reach no pain: descriptive and inferential analysis will be conducted based on the data obtained in between baseline and final visit assessments.
- Normalized Sum of Pain relief (TOTPAR₀₋₅): the descriptive and inferential analyses will be conducted for Day 5.
- Time course of PID and time course of Pain relief (VRS): descriptive analysis will be conducted for the observed values from baseline to Day 5.
- Frequency of Adverse Events: descriptive analysis will be conducted based on the data obtained in between baseline and final visit.

The inferential analysis for the Normalized Sum of Pain Intensity Difference (SPID₀₋₅), Roland-Morris Disability Questionnaire^[5] (RMDQ) score, Mobility evaluation^[6,7], Normalized Sum of Pain relief (TOTPAR₀₋₅), will be based on the analysis of covariance (ANCOVA) model with the group (patch, no-patch) as fixed effect and baseline pain intensity as a continuous covariate. The Least-Square Means, Standard Errors and 95% Confidence Intervals for each group (patch, no-patch) will be estimated and provided, along with the Least-Square Means, Standard Errors and 95% Confidence Intervals for the difference between group with patch and no-patch group. Additional effects will be added to the model in case of need.

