3.3 General guideline for inferential analysis

All statistical tests will be conducted at 2-sided using 5% alpha level.

The inferential analysis of quantitative variables based on analysis of covariance (ANCOVA) model with the treatment group as fixed effect and baseline instantaneous pain NRS as a continuous covariate will be conducted with estimating and providing the Least-Square Means (LS Means), Standard Errors (SE) and 95% Confidence Intervals (CI) for each treatment group along with the LS Means, SE and 95% CI for the difference between treatment groups. Additional effects will be added to the model in case of need and described in CSR.

The inferential analysis of time-to-event endpoints will include summary, survival curves, and analysis using Kaplan-Meier estimation method. The comparison of survival distributions between treatment groups will be done by the Log-Rank test.

The inferential analysis of key secondary endpoints will be adjusted for multiplicity using a False Discovery Rate approach (Benjamini-Hochberg) within a separate analysis table that will consist nominal and adjusted p-values. Tables with original inferential key secondary analyses will be presented with the nominal p-values.

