4.1.3 Full Analysis Set (FAS)

The FAS population will be defined as all subjects randomized that had the NRS evaluation done at baseline and that were not using any rescue medication (as defined in Section 5.1.7.4.2) starting from randomization to Day 5 Visit 2 or starting before the study and still ongoing at randomization with the exclusion of subjects without any pain at baseline (i.e. baseline instantaneous pain NRS score equal to "0"). This population will be used for key secondary, other secondary and exploratory analyses.

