5.1.7.2 Key Secondary Analyses

Key Secondary analyses will be based on the FAS population.

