5.1.7.2.2 Mobility Evaluation

Mobility evaluation (Schober's Test score and Fingertip to Floor Test score) will be summarized for actual values and change from baseline with descriptive statistics by treatment group and by visit (Baseline Visit 1, Day 5 Visit 2). Change from baseline for mobility evaluation scores will be analyzed by ANCOVA model with the treatment group as fixed effect and baseline instantaneous pain NRS as a continuous covariate.

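### The key secondary mobility ANCOVA adjusts for baseline pain but not for baseline mobility, which is measured at Visit 1, so it can lose precision.

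*SAP*

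**What the plan says.** SAP 5.1.7.2.2 sets the model: "Change from baseline for mobility evaluation scores will be analyzed by ANCOVA model with the treatment group as fixed effect and baseline instantaneous pain NRS", the latter as a continuous covariate. SAP 3.3 has the same two terms for every ANCOVA endpoint. Protocol 8.3.1.2 agrees, with group as fixed effect "and baseline pain intensity as a continuous covariate".

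The Visit 1 procedures in protocol 7.6.1 include "Baseline mobility assessment (physician"), so the baseline value exists for the same visit as baseline pain. The analysis uses it only in the descriptive summary and to form the change score.

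SAP 3.3 leaves the model open: "Additional effects will be added to the model in case of need and described in CSR". It names no covariate and no trigger. SAP 5.1.11, which lists departures from the protocol, does not mention baseline mobility.

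Two related points affect the fix. SAP 5.1.7.2.2 refers to both instruments ("Test score and Fingertip to Floor Test score"), whereas protocol 6.3.2 offers one or the other ("Test or Fingertip to Floor Test) are described in Section 17.2"). On the analysis set, the SAP says "Key Secondary analyses will be based on the FAS population", and SAP 4.1.3 limits that set to subjects who "were not using any rescue medication (as defined in Section 5.1.7.4.2) starting from randomization to Day 5 Visit 2" (or with use ongoing at randomization). Protocol 8.3.1.2 names the ITT population for the same analyses.

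**The concern.** A change-score model without the baseline value assumes that each unit of baseline mobility carries over fully to Day 5. If the true slope is below 1, part of the between-subject variation in change is predictable from baseline mobility and is left in the error term. ANCOVA with the outcome's own baseline estimates that slope and removes the variation. The SAP already does this for pain: the SPID model in SAP 5.1.7.2.1 adjusts for the same baseline NRS from which PID is computed. Mobility is adjusted for the baseline of a different instrument instead.

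Mobility is a named secondary objective and belongs to the key secondary family under Benjamini-Hochberg control. A wider confidence interval than the data allow is a real cost, though a limited one: no power is claimed for this endpoint, and SAP 5.1.7.2.5 treats its p-value as confirmatory only if the primary endpoint succeeds. The open clause in SAP 3.3 does not solve the problem, because in an open-label trial it allows covariates to be chosen after results are seen.

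**Working it through.** **The plan's own figure.** The 90 per arm in SAP 2.4 is for the responder endpoint. For 20% vs 39%, two-sided 5%, pooled normal approximation: null SE = √(2 × 0.295 × 0.705 / 90) = 0.0680; alternative SE = √((0.16 + 0.2379) / 90) = 0.0665; z = (0.19 − 1.96 × 0.0680) / 0.0665 = 0.85; power 80.3%. Also 180 / 0.90 = 200. The figure reproduces, but it says nothing about mobility.

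**Inputs for mobility (all assumed).** r = correlation of baseline with Day 5 mobility; ρ = correlation of baseline pain with baseline mobility. In the base case the SDs are equal (set to 1) and pain relates to Day 5 mobility only through baseline mobility, so its correlation with Day 5 is rρ.

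**Formula.**
- Planned model: var(change | pain) = 2(1 − r) − ρ²(1 − r)² = (1 − r)[2 − ρ²(1 − r)]
- With own baseline added: var(Day 5 | baseline mobility, pain) = 1 − r²
- Ratio = [2 − ρ²(1 − r)] / (1 + r)

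Example, r = 0.5, ρ = 0.3: (2 − 0.045) / 1.5 = 1.30.

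| r | ratio, ρ = 0 | ρ = 0.3 | ρ = 0.5 | CI widening (ρ = 0.3) | 90 per arm worth (90 / ratio, ρ = 0.3) |
|---|---|---|---|---|---|
| 0.5 | 1.33 | 1.30 | 1.25 | 14% | 69 |
| 0.7 | 1.18 | 1.16 | 1.13 | 8% | 78 |
| 0.8 | 1.11 | 1.10 | 1.08 | 5% | 82 |
| 0.9 | 1.05 | 1.05 | 1.04 | 2% | 86 |

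At r = 0.4 and ρ = 0 the ratio is 2 / 1.4 = 1.43, so over r 0.4 to 0.8 the excess variance is 8% to 43%.

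**Power** for an assumed effect of 0.4 mobility SD, ρ = 0.3, 90 per arm, noncentral t, planned model vs own baseline added: 77% vs 87% (r 0.5), 85% vs 92% (r 0.6), 93% vs 96% (r 0.7), 99% vs 99% (r 0.8).

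**Looser assumptions**, using the full 3 × 3 covariance matrix:
- Pain correlations with baseline and Day 5 mobility each 0 to 0.5: 1.21–1.70 (r 0.4), 1.12–1.56 (r 0.5), 1.01–1.36 (r 0.7), 1.00–1.36 (r 0.8).
- Day 5 SD 0.8 to 1.2 times baseline SD, ρ = 0.3: 1.20–1.78 (r 0.4), 1.13–1.68 (r 0.5), 1.03–1.54 (r 0.7), 1.00–1.51 (r 0.8).

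The ratio reaches 1.00 where the slope of Day 5 on baseline mobility, given pain, is 1. It does not fall below 1, apart from one degree of freedom.

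**Simulation without selection** (4000 trials, 90 per arm, ρ = 0.3, no effect): ratio 1.29 (r 0.5) and 1.16 (r 0.7); rejection 4.7–5.5% in both models. The omission does not distort the type I error of an as-randomized comparison.

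**Simulation on an FAS-like set.** 15% (patch) and 40% (no patch) are removed for rescue by a latent score correlated 0.5 with mobility, which leaves about 77 and 54 subjects. Rates are assumed; there is no true effect. Results at r 0.5 and 0.7:

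| Removal depends on | Planned model: bias (SD), rejection | Own baseline added |
|---|---|---|
| Baseline mobility | −0.09 and −0.05; 7.8% and 6.8% | bias removed; 5.0% and 5.1% |
| Day 5 mobility | 0.10 and 0.06; 8.4% and 7.8% | 0.14 and 0.10; 15.7% and 12.8% |

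With equal 20% removal in both arms, rejection is 4.5–5.2% in both models. The covariate can therefore reduce or enlarge a selection bias, depending on what drives rescue use.

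**The case against.** Protocol and SAP agree on a prespecified model that is valid under randomization, so this is a loss of efficiency and not an error. Every correlation, SD ratio and effect size is assumed, and the gain can be nil: at r 0.8 and ρ 0.3 power is 99% either way. All of that stands, and it limits the weight of the point.

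The 90-per-arm levels are also too favourable, because the FAS drops rescue users. With 77 and 54 subjects and selection bias ignored, power at r 0.5 is 62% vs 73%. The levels fall but the gap remains.

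The strongest objection is that the benefit is shown for an as-randomized comparison, whereas the SAP plans an analysis on a set selected after randomization, where the covariate could increase bias. That is a reason not to present the covariate as a cure. It is not a reason to leave it out: the simulated bias comes from unequal selection, arises in both models, and disappears in both when removal is equal.

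Finally, the RMDQ model and the exploratory pain models also omit their own baselines. That is a fair remark on scope, but it does not weaken the point for mobility.

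**Conclusion.** The point holds as a modest matter of precision on a key secondary endpoint. The covariate is collected, is absent from the prespecified model, and is not supplied by the open clause in SAP 3.3. In the base case with ρ = 0.3, the planned model's confidence interval is 14% wider at r 0.5, 8% at r 0.7, 5% at r 0.8 and 2% at r 0.9. Under the looser assumptions the variance ratio lies anywhere from 1.00 to 1.78 for r between 0.4 and 0.8. The documents cannot narrow this range. The omission does not bias an as-randomized comparison. On the FAS, freedom from bias cannot be assured with or without the covariate. The primary analysis and its sample size are unaffected.

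**What to change.** In SAP 3.3 and 5.1.7.2.2, name baseline mobility as a covariate alongside baseline pain NRS. Define it as the Visit 1 value of the same test, with a separate model for each test, since the SAP lists both. Record the departure from protocol 8.3.1.2 in SAP 5.1.11, dated before database lock.

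Do not describe the covariate as a remedy for the exclusion of rescue users. The choice between the FAS and the protocol's ITT set must be settled separately. No change to the RMDQ or exploratory pain models is asked for here. Optionally, state how a baseline RMDQ score of 0 is handled, with a count by arm, because the percent-change formula in SAP 3.1 divides by baseline.

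The cost is one model term from data already collected, with no new assessment and no change of endpoint. The constraint is timing: the SAP is at version 4.0 in an open-label trial, so the change is clean only if it is signed off before lock, as protocol section 8 requires of the SAP.

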5.1.7.2.3 Roland-Morris Disability Questionnaire

Subject's Roland-Morris Disability Questionnaire (RMDQ) score will be defined as the total number of out of 24 statements from RMDQ questionary that subject marked as appropriate (result "Yes" in e-diary).

RMDQ score will be summarized for actual values and percent change from baseline with descriptive statistics by treatment group and by analysis timepoint (Baseline Visit 1, Day 5 Visit 2). Percent change from baseline for RMDQ score will be analyzed by ANCOVA model with the treatment group as fixed effect and baseline instantaneous pain NRS as a continuous covariate.

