6.4.5 Inclusion Criteria

Subjects will be eligible to participate in the study if **all** of the following conditions exist:

- 1. Male or female subjects who are ≥ 18 years and < 65 years.
- 2. Subjects suffering from mild to moderate acute low back pain.

- Low back pain (lumbar back pain) is defined as pain in the back from the level of the lowest rib down to the gluteal fold.
 - Acute episode is defined as acute pain with less than 1 month duration.
- With intensity ≤ 6 on 0-10 Numerical Rating Scale (NRS).

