17.1 Roland-Morris Low Back Pain and Disability Questionnaire

The Roland-Morris Disability Questionnaire (RMDQ) is a self-administered disability measure in which greater levels of disability are reflected by higher numbers on a 24-point scale. The RMDQ has been shown to yield reliable measurements, which are valid for inferring the level of disability, and to be sensitive to change over time for groups of subjects with low back pain.

Interpretation of scores

Roland and Morris did not provide descriptions of the varying degrees of disability (e.g. 40%-60% is severe disability). Clinical improvement over time can be graded based on the analysis of serial questionnaire scores. If, for example, at the beginning of treatment, a subject's score was 12 and, at the conclusion of treatment, their score was 2 (10 points of improvement), we would calculate an 83% ($10/12 \times 100$) improvement.

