2.2.2 Secondary Endpoints

The Secondary endpoints of this study are listed below:

- 1. normalized Sum of Pain Intensity Difference (PID, which equals the instantaneous NRS change from baseline) over 5 days (SPID₀₋₅);
- 2. Roland-Morris Disability Questionnaire (RMDQ) score improvement (%) from baseline to Day 5;
- 3. mobility evaluation: change from baseline to Day 5;
- 4. time to reach acceptable pain;
- 5. time to reach no pain (NRS = 0);
- 6. time course of PID over time from baseline to Day 5 on-site evaluation;
- 7. time course of Pain relief over time from baseline to Day 5 (VRS);
- 8. normalized Sum of Pain relief over 5 days (TOTPAR₀₋₅).

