3 DATA ANALYSIS CONSIDERATION

3.1 General Considerations

The statistical analyses will be performed using SAS Version 9.4 (or higher). All tables, figures and listings will be produced in landscape format.

Data will be presented at each scheduled timepoint (nominal time), where applicable.

Unless otherwise specified, the baseline will be defined as the last non-missing assessment prior to patch application (FIRTECH Patch) or randomization (No Patch) at Day 1 Visit 1.

The change from baseline will be calculated as the following:

Change from Baseline
$$=$$
 (Observed Value) $-$ (Baseline Value).

The percent change from baseline will be calculated as the following:

Percent Change from Baseline (%) =
$$\frac{(Observed\ Value) - (Baseline\ Value)}{(Baseline\ Value)} * 100\%.$$

The total number of subjects in the study group (N) under the stated set of subjects will be displayed in the header of summary tables.

All study data will be included in the study data listings. Listings will be displayed by subject in chronological order, if not stated otherwise.

For tabulated summaries, only the scheduled visits will be included in the summary tables. Unscheduled assessments will be listed.

Medications will be coded with the WHO drug dictionary (WHO Drug global B3 September 2021). Medical History, Adverse Events, and Non-drug therapies will be coded using Medical Dictionary for Regulatory Activities (MedDRA, version 24.1). The dictionary versions will remain the same throughout the course of the study.

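### The RMDQ test on percent change has no value at a baseline score of 0 and gives heavy weight to worsening from low baselines; change in points adjusted for baseline RMDQ avoids both

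*SAP*

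**What the plan says.** SAP 5.1.7.2.3 defines the RMDQ score as "the total number of out of 24 statements from RMDQ questionary that subject marked as appropriate", so it is a whole number from 0 to 24. Protocol 17.1 gives the direction: "greater levels of disability are reflected by higher numbers on a 24-point scale".

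The endpoint in Protocol 6.3.2 and SAP 2.2.2 is "Roland-Morris Disability Questionnaire (RMDQ) score improvement (%) from baseline to Day 5". SAP 5.1.7.2.3 carries this into the model: "Percent change from baseline for RMDQ score will be analyzed by ANCOVA model with the treatment group as fixed effect". The other term is "baseline instantaneous pain NRS as a continuous covariate"; baseline RMDQ is not in the model. The general rule in SAP 3.1 ("The percent change from baseline will be calculated as the following") is change divided by the baseline value, times 100, and it says nothing about a baseline of 0.

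Entry under Protocol 6.4.5 is for "Subjects suffering from mild to moderate acute low back pain", with an NRS ceiling of 6 and no lower limit. Neither 6.4.5 nor 6.4.6 sets a minimum RMDQ. SAP 4.1.2 and 4.1.3 remove subjects with a baseline NRS of 0 from the mITT and the FAS. No matching rule exists for RMDQ. The RMDQ is summarised as actual values and percent change; change in points is neither tabulated nor tested.

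**The concern.** A ratio with the baseline in the denominator suits a score that stays well away from 0. Nothing in this plan ensures that. A subject with some pain (NRS 1 to 6) and no ticked RMDQ item is eligible and belongs to the FAS, yet has no value for the tested variable and leaves the ANCOVA without any rule saying so. Such a subject can only stay the same or get worse, and neither outcome would be counted.

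Subjects just above 0 pose the opposite problem. A shift of a few items becomes a change of several hundred percent, and a least-squares model gives that subject great influence on the arm mean and the residual variance.

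RMDQ is the only measure for the secondary disability objective. It is one of four key secondary endpoints in the Benjamini-Hochberg family, and SAP 5.1.7.2.5 reads that family as confirmatory if the primary succeeds.

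**Working it through.** **The plan's own figure.** Protocol 17.1 gives an example in which "a subject's score was 12 and, at the conclusion of treatment, their score was 2 (10 points of improvement"). Then 10/12 = 83.3%, which matches the stated 83%. The documents give no RMDQ mean, SD, effect size or power, so there is nothing else to reproduce.

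**Range of the tested variable.** Percent change = (Day 5 - b)/b x 100, with b the baseline score.

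- b = 0: the denominator is 0, so there is no value.
- Best case (Day 5 = 0): -100% for every b above 0.
- Worst case (Day 5 = 24): (24 - b)/b x 100. This gives +2300% at b = 1, +1100% at 2, +700% at 3, +300% at 6 and +100% at 12.

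**Weight of one subject.** A move from 1 to 5 is +400%. It shifts the mean of a 90-subject arm by 400/90 = 4.4 percentage points, and of a 50-subject arm by 400/50 = 8.0. The FAS also excludes users of rescue medication, so arms may be smaller than 90. The extreme, 1 to 24, shifts a 90-subject arm by 2300/90 = 25.6.

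**Power, by simulation.** Every input here is an assumption; none comes from the documents. There were 2000 trials per setting, two-sided 5%, with a Monte Carlo error of about 2 points. Three models are compared: P = percent change with NRS (the plan, b above 0 only); D = change in points with NRS; DB = change in points with NRS and baseline RMDQ.

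Settings A and B: 80 per arm, baseline a rounded normal cut to 0-24, true reduction 35% without and 50% with the patch. Noise is a constant SD of 3 points in A, and an SD of 38% of baseline in B.

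| Baseline mean/SD | A: P / D / DB | DB - P | B: P / D / DB | DB - P |
|---|---|---|---|---|
| 6/4 | 22 / 40 / 51 | +29 | 62 / 43 / 54 | -8 |
| 8/5 | 32 / 60 / 75 | +43 | 63 / 46 / 56 | -7 |
| 10/5 | 51 / 77 / 88 | +37 | 66 / 50 / 59 | -7 |
| 12/5 | 72 / 91 / 97 | +25 | 68 / 56 / 62 | -6 |

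Settings C and D: 90 per arm, beta-binomial baseline. C has a proportional effect of 15 percentage points with mixed noise (SD 30% of baseline plus a constant SD of 1.5 points). D has an additive effect of 1.5 points with a constant SD of 3.5 points.

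| Baseline mean | C: P / D / DB | DB - P | D: P / D / DB | DB - P |
|---|---|---|---|---|
| 4 | 22.4 / 28.9 / 43.2 | +20.8 | 49.3 / 53.3 / 61.2 | +11.9 |
| 6 | 35.4 / 41.2 / 59.8 | +24.4 | 56.5 / 64.4 / 67.6 | +11.1 |
| 8 | 49.8 / 56.0 / 69.0 | +19.2 | 59.0 / 69.8 / 72.1 | +13.1 |
| 11 | 73.9 / 70.2 / 78.0 | +4.1 | 68.1 / 77.6 / 78.4 | +10.3 |
| 14 | 85.8 / 80.0 / 85.4 | -0.4 | 73.5 / 80.9 / 81.1 | +7.6 |

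**Scale or covariate.** In A the scale (D - P) gives 18 to 28 points and the covariate (DB - D) 6 to 15. In C at means 4 to 8 the scale gives about 6 and the covariate about 13 to 19. In A, adding baseline RMDQ to the percent model leaves its power unchanged (22, 32, 52 and 72%), so the covariate alone does not repair the planned scale.

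**Share at baseline 0.** In A and B it is about 1 to 8%. In C and D it is about 18, 7, 3, 0.3 and 0% at means 4, 6, 8, 11 and 14.

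**Type I error.** With no true effect (C with equal arms, 60 or 90 per arm), the planned model rejects in 4.0 to 6.3% of trials.

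**The case against.** The percent scale is the protocol's choice: it is in the endpoint definition, in the inferential analysis of Protocol 8.3.1.2 and in the worked example, and the SAP follows it. Replacing a defined key secondary endpoint late in an open-label trial is not trivial. This stands, and it is why the change must be written down before lock and the percent measure kept.

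A reader might infer that worsening is unbounded. It is not: the score stops at 24.

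A reader might also infer that the plan certainly loses power, or that the percent scale is the main cause. The documents support neither. Setting B reverses the direction. In another assumed model, where baseline items either persist or clear and no one can worsen, the planned analysis does as well as the alternative (79% vs 78% at 6/4, 91% vs 89% at 12/5). In C much of the gain comes from the covariate.

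The share of low baselines is unknown and may be small. Actual scores are summarised by arm and listed per subject, so an extreme value could be seen after the fact. Extra model effects are permitted by SAP 3.3 if needed, but that neither names baseline RMDQ nor defines a value at baseline 0.

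**Conclusion.** The concern holds in two parts that need no assumption. The tested variable does not exist at baseline RMDQ 0, which the plan allows, and the scale gives worsening from low baselines far more weight than any improvement can receive.

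The effect on power is conditional. Under constant or mixed noise, or an additive effect, the planned model loses mostly between about 4 and 43 points, and nothing in the mixed setting at mean 14. Under noise purely proportional to baseline it gains about 5 to 9.

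A reader might infer a biased or invalid comparison; that does not follow. Exclusion at baseline 0 depends on a score taken before randomisation, and the simulated type I error stays near 5%. The cost is lost subjects, a mean that a few near-normal subjects can move, and possibly power. It is confined to one key secondary endpoint, for which no power is claimed, and does not touch the primary.

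**What to change.** Before database lock, change SAP 5.1.7.2.3 so that:

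- the tested analysis is an ANCOVA of change in RMDQ points (Day 5 minus baseline) with arm, baseline RMDQ and baseline NRS;
- the LS mean difference in points is reported with its 95% CI, and this p-value enters the Benjamini-Hochberg table;
- improvement (%) stays as a descriptive row for subjects with a baseline above 0, with the number at baseline 0 shown by arm.

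Record the departure from the protocol's percent definition in SAP 5.1.11, with the reason.

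The cost is a short text change and one model statement; all data are already collected. The downside is that the tested scale would differ from the protocol-defined one, and could be slightly less powerful if variability is purely proportional to baseline.
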